^c Resumption of atezolizumab may be considered in patients who are deriving benefit and have fully recovered from the immune-mediated event. Patients can be re-challenged with atezolizumab only after approval has been documented by both the investigator (or an appropriate delegate) and the Medical Monitor.

Appendix 8
Risks Associated with Atezolizumab and Guidelines for
Management of Adverse Events Associated with Atezolizumab
(cont.)

Table 13 Management Guidelines for Immune-Mediated Myositis (cont.)

Immune-mediated myositis, Grade 3	
 • Withhold atezolizumab for up to 12 weeks after event onset^a and contact Medical Monitor. • Refer patient to rheumatologist or neurologist. • Initiate treatment as per institutional guidelines. • Respiratory support may be required in more severe cases. • Initiate treatment with corticosteroids equivalent to 1–2 mg/kg/day IV methylprednisolone, or higher-dose bolus if patient is severely compromised (e.g., cardiac or respiratory symptoms, dysphagia, or weakness that severely limits mobility); convert to 1–2 mg/kg/day oral prednisone or equivalent upon improvement. • If event does not improve within 48 hours after initiating corticosteroids, consider adding an immunosuppressive agent. • If event resolves to Grade 1 or better, resume atezolizumab.^b • If event does not resolve to Grade 1 or better while withholding atezolizumab, permanently discontinue atezolizumab and contact Medical Monitor.^c • For recurrent events, treat as a Grade 4 event.
Immune-mediated myositis, Grade 4	
 • Permanently discontinue atezolizumab and contact Medical Monitor.^c • Refer patient to rheumatologist or neurologist. • Initiate treatment as per institutional guidelines. • Respiratory support may be required in more severe cases. • Initiate treatment with corticosteroids equivalent to 1–2 mg/kg/day IV methylprednisolone, or higher-dose bolus if patient is severely compromised (e.g., cardiac or respiratory symptoms, dysphagia, or weakness that severely limits mobility); convert to 1–2 mg/kg/day oral prednisone or equivalent upon improvement. • If event does not improve within 48 hours after initiating corticosteroids, consider adding an immunosuppressive agent. • If event resolves to Grade 1 or better, taper corticosteroids over ≥ 1 month.

^a Atezolizumab may be withheld for a longer period of time (i.e., > 12 weeks after event onset) to allow for corticosteroids (if initiated) to be reduced to the equivalent of ≤ 10 mg/day oral prednisone. The acceptable length of the extended period of time must be agreed upon by the investigator and the Medical Monitor.

^b If corticosteroids have been initiated, they must be tapered over ≥ 1 month to the equivalent of ≤ 10 mg/day oral prednisone before atezolizumab can be resumed.

^c Resumption of atezolizumab may be considered in patients who are deriving benefit and have fully recovered from the immune-mediated event. Patients can be re-challenged with atezolizumab only after approval has been documented by both the investigator (or an appropriate delegate) and the Medical Monitor.

Appendix 8

Risks Associated with Atezolizumab and Guidelines for Management of Adverse Events Associated with Atezolizumab (cont.)

HEMOPHAGOCYTIC LYMPHOHISTIOCYTOSIS AND MACROPHAGE ACTIVATION SYNDROME

Immune-mediated reactions may involve any organ system and may lead to hemophagocytic lymphohistiocytosis (HLH) and macrophage activation syndrome (MAS).

Patients with suspected HLH should be diagnosed according to published criteria by McClain and Eckstein (2014). A patient should be classified as having HLH if five of the following eight criteria are met:

- Fever $\geq 38.5^{\circ}\text{C}$
- Splenomegaly
- Peripheral blood cytopenia consisting of at least two of the following:
 - Hemoglobin $< 90 \text{ g/L}$ (9 g/dL) ($< 100 \text{ g/L}$ [10 g/dL] for infants < 4 weeks old)
 - Platelet count $< 100 \times 10^9/\text{L}$ ($100,000/\mu\text{L}$)
 - ANC $< 1.0 \times 10^9/\text{L}$ ($1000/\mu\text{L}$)
- Fasting triglycerides $> 2.992 \text{ mmol/L}$ (265 mg/dL) and/or fibrinogen $< 1.5 \text{ g/L}$ (150 mg/dL)
- Hemophagocytosis in bone marrow, spleen, lymph node, or liver
- Low or absent natural killer cell activity
- Ferritin $> 500 \text{ mg/L}$ (500 ng/mL)
- Soluble interleukin 2 (IL-2) receptor (soluble CD25) elevated ≥ 2 standard deviations above age-adjusted laboratory-specific norms

Patients with suspected MAS should be diagnosed according to published criteria for systemic juvenile idiopathic arthritis by Ravelli et al. (2016). A febrile patient should be classified as having MAS if the following criteria are met:

- Ferritin $> 684 \text{ mg/L}$ (684 ng/mL)
- At least two of the following:
 - Platelet count $\leq 181 \times 10^9/\text{L}$ ($181,000/\mu\text{L}$)
 - AST $\geq 48 \text{ U/L}$
 - Triglycerides $> 1.761 \text{ mmol/L}$ (156 mg/dL)
 - Fibrinogen $\leq 3.6 \text{ g/L}$ (360 mg/dL)

Patients with suspected HLH or MAS should be treated according to the guidelines in [Table 14](#).

Appendix 8
Risks Associated with Atezolizumab and Guidelines for
Management of Adverse Events Associated with Atezolizumab
(cont.)

Table 14 Management Guidelines for Suspected Hemophagocytic Lymphohistiocytosis or Macrophage Activation Syndrome

Event	Management
Suspected HLH or MAS	
 • Permanently discontinue atezolizumab and contact Medical Monitor. • Consider patient referral to hematologist. • Initiate supportive care, including intensive care monitoring if indicated per institutional guidelines. • Consider initiation of IV corticosteroids and/or an immunosuppressive agent. • If event does not improve within 48 hours after initiating corticosteroids, consider adding an immunosuppressive agent. • If event resolves to Grade 1 or better, taper corticosteroids over ≥ 1 month.

HLH=hemophagocytic lymphohistiocytosis; MAS=macrophage activation syndrome.

REFERENCES

Version 3 / 20 April 2018	
 • Clarified exclusion from this SAP of antibody analysis, pharmacokinetic analysis as well as exploratory biomarker analysis • Removed modified RECIST analysis • Rescheduled Stage II analysis to be part of combined Month 12 analysis • Clarified analysis set definitions • Added waterfall plot • Clarified DOR will only be analyzed if >3 patients with CR/PR in the cohort • Simplified summary of study drug exposure (removed dose intensity and detailed summaries of delayed infusions) • Specified AESIs defined by Roche current standard (superseding eCRF tickbox) • Removed most listings (exceptions include deaths, SAEs and AESIs)
Version 4.0 / 12 February 2020	
 • Added more information about calculation of missed and delayed doses • Allowed for minor departures from 12 patients at Stage I analysis time • Removed Koyama and Chen adjustment of Stage II analysis of NPR (not directly applicable in case of departure from intended Stage I sample size) • Updated extended time window for NPR at 18 weeks (section 4.4.1): extended window to define imputed CR/PR/SD increased up to Day 209 (as for NPR at 24 weeks) • Analysis of modified RECIST added (BOR only) • PK and ADA analyses added • Biomarker (PD-L1) analysis added. • Clarifications added on the analysis of all cohorts combined

TABLE OF CONTENTS

STATISTICAL ANALYSIS PLAN HISTORY	3
1. BACKGROUND	6
2. STUDY DESIGN	6
2.1 Objectives	8
2.2 Determination of Sample Size.....	9
2.2.1 Definition of Cohorts and Extensions/Expansions	10
2.3 Analysis Timing.....	11
3. STUDY CONDUCT.....	12
4. STATISTICAL METHODS	13
4.1 Analysis SETS	13
4.1.1 Intention-to-treat Set	13
4.1.2 Safety Set.....	14
4.1.3 Analysis sets for efficacy analyses.....	14
4.1.3.1 Eligibility and evaluability	14
4.1.3.2 Stage I Efficacy Set	14
4.1.3.3 Stage II (and Subsequent) Efficacy Set	14
4.2 Summaries of Study Conduct	14
4.3 Summaries of Treatment Group Comparability.....	15
4.4 Efficacy Analysis	15
4.4.1 Primary Efficacy Endpoint	15
4.4.2 Analysis of the Primary Efficacy Endpoint	16
4.4.3 Secondary Efficacy Endpoints	16
4.4.4 Analysis of the Secondary Efficacy Endpoints	18
4.4.4.1 Analysis of NPR, BOR, ORR and CBR	18
4.4.4.2 Response and lesion assessments	18
4.4.4.3 Time to event analyses.....	19
4.5 Pharmacokinetic (PK) Analysis	19
4.6 Immunogenicity Analysis.....	19
4.7 Safety Analyses	20
4.7.1 Exposure to Study Medication	20
4.7.2 Adverse Events	20

4.7.3	Laboratory Data	21
4.7.4	Vital Signs and ECG	21
4.8	Biomarker Analysis	21
4.9	Missing Data	22
5.	REFERENCES	22

1. **BACKGROUND**

This study will assess the efficacy and safety of the anti-PDL1 therapeutic antibody Atezolizumab for the treatment of various advanced solid tumors. The tumors included in this study are listed in Section 2 below. A brief description of their epidemiology and prognoses is presented in Table 1 of the Protocol (Section 1.1).

2. **STUDY DESIGN**

This is an open-label, multicenter, multinational, multi-cohort, phase II study. For each patient, the study will consist of a Screening Period (Day –35 to –1), a Treatment Period, and a Treatment Discontinuation Visit occurring ≤ 30 days after the last dose of study medication. Each cohort will be followed for survival until 2 years after the first dose for the final patient in the cohort. For further illustration please see Figure 1 on study schema in the protocol.

The study will include cohorts of patients with the following solid tumors (see Protocol version 8):

- 1) Cervical cancer
- 2) Nasopharyngeal carcinoma
- 3) Known high microsatellite instability (MSI-H) or mismatch repair (MMR) deficient colorectal cancer
- 4) Known BRCA 1/2 mutated cancers
 - a) BRCA mutated ovarian cancer
 - b) BRCA mutated breast cancer and that are not characterized as triple negative breast cancer
- 5) Soft tissue and visceral sarcoma
 - a) Liposarcoma
 - b) Leiomyosarcoma
 - c) Gastrointestinal stromal tumor (GIST)
 - d) Undifferentiated pleomorphic sarcoma and
 - e) Known translocation related sarcomas
 - f) Radiation induced sarcoma
 - g) Osteosarcoma
 - h) Chondrosarcoma
- 6) Mesothelioma
 - a) Pleural mesothelioma

- b) Peritoneal mesothelioma
- 7) Cholangiocarcinoma/cancer of the biliary tract
- 8) Thyroid cancer
 - a) Anaplastic thyroid cancer
 - b) Follicular or papillary thyroid cancer
 - c) Medullary thyroid cancer and mixed medullary and follicular or papillary thyroid cancer
- 9) Gastric adenocarcinoma/adenocarcinoma of the gastro-esophageal junction (GEJ)
- 10) Other solid tumors – closed to recruitment from Protocol Version 4 onwards
- 11) Malignant germ cell tumors
- 12) ER+/HER2- metastatic breast cancer with known high mutation load (>100 mutations) by local test
- 13) Thymoma and thymic cancer
 - a) Thymoma
 - b) Thymic cancer
- 14) Gastroenteropancreatic (GEP) and lung neuroendocrine tumors (NETs)
 - a) Low and intermediate grades (typical or atypical carcinoid)
 - b) Poorly differentiated grade (excluding SCLC)
- 15) Known HPV induced squamous cell carcinoma
 - a) Head and Neck
 - b) Penile cancer
 - c) Vaginal cancer/ vulvar cancer
 - d) Anal cancer
- 16) Known MSI high or MMR deficient tumors (excluding colorectal and gastric cancers)

Enrollment in this study will be based on Simon's optimal two-stage design (Simon, 1989). The primary objective of this study is to evaluate investigator-determined non-progression rate (NPR) at 18 weeks in the individual cohorts.

2.1 OBJECTIVES

Efficacy Objectives

The primary efficacy objective for this study is as follows:

To evaluate non-progression rate (NPR) at 18 weeks in patients with advanced solid tumors treated with Atezolizumab, defined as the percentage of patients with complete response (CR) partial response (PR) or stable disease (SD) as assessed by the Investigator¹. The secondary efficacy objectives for this study are as follows:

- To evaluate NPR at 24 weeks, overall response rate (ORR), best overall response (BOR), clinical benefit rate (CBR), duration of response (DOR), time to tumor progression (TTP) and progression-free survival (PFS), as assessed by the Investigator¹.
- To evaluate NPR at 18 and 24 weeks, ORR, BOR, CBR, DOR, TTP and PFS, as assessed by the Investigator using *modified RECIST*²
- To evaluate overall survival (OS)

Safety Objectives

The safety objectives for this study are as follows:

- To evaluate the safety and tolerability of Atezolizumab in patients with advanced solid tumors
- To characterize the immunogenic potential of Atezolizumab by measuring anti-Atezolizumab antibodies and to explore the potential relationship of the immunogenicity response with safety and efficacy

Pharmacokinetic Objectives

The pharmacokinetic (PK) objectives for this study are as follows:

¹ That is, using disease progression status as recorded in the clinical database. Investigator assessments are carried out according to Response Evaluation Criteria In Solid Tumors, Version 1.1 (RECIST, v1.1) (except for prostate cancer and malignant pleural mesothelioma) and disease-specific criteria for patients with prostate cancer (see Protocol Appendix 6) and malignant pleural mesothelioma (see Protocol Appendix 7).

² That is, using disease progression status as recorded in the clinical database, for Investigator assessments carried out according to *modified RECIST* criteria as defined in Protocol Appendix 3.

- To characterize the pharmacokinetics of Atezolizumab

Exploratory Objectives

The exploratory objectives for this study are as follows:

- To evaluate the relationship between tumor tissue PD-L1 expression and measures of efficacy, including NPR at 18 weeks and 24 weeks, ORR, BOR, CBR, DOR, TTP, PFS and OS
- To assess predictive and prognostic exploratory biomarkers(e.g. but not limited to protein and genetic markers on DNA and RNA) in archival and/or fresh tumor tissue and plasma and their association with disease status and/or response to study treatment
- To evaluate exploratory pharmacodynamic (PD) biomarkers (e.g., genetic markers, T, B and NK cell enumeration, T cell subpopulations like CD8+ T, effector/memory T cells, regulatory T cells, changes in expression of CD25 or human leukocyte antigen-DR [HLA-DR], interferon [IFN]-gamma production,IL-2 and other exploratory biomarkers) in tumor tissue, tumor microenvironment and plasma and their association with disease status, and/or response to study treatment, tumor immunobiology or tumor type

2.2 DETERMINATION OF SAMPLE SIZE

The sample size for this phase II study is based on Simon's optimal two-stage design (Simon, 1989).

In this Phase II study, an NPR of 20% is a level of activity that is not of interest for further clinical development, whereas an NPR of 40% is of clinical interest. The type I error will be 10% and the study will have 80% power to reject the null hypothesis when the true NPR is 40%.

The Simon design in this study requires 12 fully evaluable patients for first stage. If at the end of the first stage there are only 0, 1 or 2 patients with non-progressive disease at Week 18, the enrollment into this cohort will be terminated (or the cohort may be expanded as described below). Otherwise, if more than 2 patients with non-progressive disease are observed at the end of Stage I, an additional 13 fully-evaluable patients will be enrolled into Stage II. The study drug will be considered of clinical interest in this cohort if, at the end of the second stage, there are 8 or more patients with non-progressive disease out of 25 total fully-evaluable patients.

It can be assumed that some patients will not be evaluable for NPR. A patient will be considered evaluable for NPR if they received study drug, have a baseline tumor assessment and at least one tumor assessment post-baseline (per protocol mandated

timelines). Thus, more than 25 patients may be needed to be enrolled to obtain 25 fully-evaluable patients.

The hypotheses and clinical assumptions will be applied to all cohorts individually.

2.2.1 Definition of Cohorts and Extensions/Expansions

Statistical analyses will be based on patients with the same individual tumor type in the protocol-defined cohorts stated in section 2 above. The cohort for each patient will be identified from the data recorded on the “Cohort Assignment” CRF record.

If, during the conduct of the study, a specific subgroup of patients in a cohort is identified, the cohort may be modified to include only that specific subgroup, and then statistical analysis may be performed based on this subgroup of patients. Subgroups of cohorts will be identified by first selecting patients in the appropriate cohort(s), and then filtering for patients meeting the required subgroup criteria.

[figure not shown]
Additionally, a subgroup that applies across multiple tumor types (e.g. a biomarker positive subgroup) may be identified to be of interest.

Cohorts of these latter types will be analyzed using the same methods as for the protocol-defined cohorts.

Statistical analyses will be performed as well on all patients from all cohorts combined. The “All combined” cohort will be analyzed using the same methods as for the protocol-defined cohorts, but won’t include the following analyses: demographics, by-patient plots, time-to-event analyses, PK, immunogenicity and biomarkers. Some of the analyses will be performed only for “All combined” (as specified throughout the SAP).

The enrollment pattern across Stage I and Stage II is shown in Figure 1 below.

Figure 1 Sample Size for Each Cohort in Stage I/II

NP = non-progressors; NPR = non-progression rate.

Assumptions: H_0 = NPR 20%; H_1 = NPR 40%; power = 80%; alpha = 10%.

The sample size was estimated using Simon's optimal two-stage design (Simon 1989).

* And no additional clinical benefit in a subgroup.

2.3 ANALYSIS TIMING

Each cohort will be analyzed independently at the following time points:

1. Stage I: when the first 12 eligible and fully evaluable patients of the cohort have passed the week 18 assessment. This analysis will focus on the primary efficacy endpoint (NPR) and a targeted subset of Safety analyses (as agreed with the Steering Committee as being sufficient for the purpose of making a decision whether or not to continue to Stage 2).
2. Month 12: for cohorts that progress to Stage 2, there may be an analysis of the majority of outcomes at Month 12 (when all patients of the cohort have been on the study for at least 12 months, have prematurely discontinued from the study or died). Such analyses are considered informative for potential future trials and early publication of individual cohort first results, but are not considered final.

3. Final analysis: the definitive Final Analysis, on which the CSR will be based, will take place following final database lock, which will be when all patients satisfy at least one of the following conditions: died, withdrawn consent or lost to follow up, or has been followed for survival for a minimum of 24 months after the last patient was enrolled, whichever occurs first. In the Final Analysis, all cohorts will be analysed both separately and combined.

3. STUDY CONDUCT

Stopping and continuation rules for Stage I:

Enrolment into the cohort will stop at the end of Stage I if the number of patients with non-progressive disease (confirmed or unconfirmed) is 2, 1 or 0 out of 12 patients. However, if the overall patient population does not meet requirements at Stage I, but a clinical benefit is observed in a specific subgroup (e.g. biomarker positive subgroup) of patients, then only this subgroup may be added for further evaluation at Stage I and Stage II.

Decisions at the end of Stage I (termination, continuation or continuation in a subgroup) will be made by the Sponsor in discussion with the study Steering Committee members.

Rules for Stage II:

A study treatment will be considered to be promising for a given cohort if:

- there is no unacceptable toxicity , and
- at 18 weeks, there are 8 or more patients with non-progressive disease out of 25 fully-evaluable patients.
- if for logistical reasons there are not exactly 25 fully-evaluable patients in a cohort, then a p-value will be calculated allowing for the departure from the planned Simon's design, using the method of Koyama and Chen (2008). By analogy with the original design being based on $\alpha=0.1$, a treatment will be considered to be promising if $p < 0.1$. This p-value can be mapped to a new cutoff point in the manner of the original design calculation. Some values for the cutoff as a function of sample size are: 7 or more out of 21 to 24; 8 or more out of 25; 9 or more out of 26 to 29; 10 or more out of 30.

If the overall patient population does not meet the Stage II criteria, but a clinical benefit is observed in a specific subgroup (e.g. biomarker positive subgroup) of patients, then

Stage II may be expanded to include additional patients from this specific subgroup in order to re-evaluate the Stage II criteria in this patient subgroup.

In all such cases where a “new” cohort is defined based on partial results from the planned cohorts, the assumptions for Simon’s design and formal hypothesis testing will not hold. Therefore, only the standard summary statistics and confidence intervals will be presented. As an informal guideline, we will consider 8 or more NPR out of 25 patients as a promising result, but to be interpreted with suitable caution.

4. STATISTICAL METHODS

Categorical data (such as discontinuation reasons or adverse events) will be summarized using frequencies and percentages (including a category for missing, if appropriate). Continuous endpoints (such as durations or concentrations) will be summarized using descriptive statistics (N, mean, standard deviation, median, lower quartile, upper quartile, minimum and maximum). Other analysis methods will be specified (below) where applicable.

Study Day 1 will be defined as the first day a patient receives study medication. Baseline values are determined by the last measurement up to and including date of treatment start (Study Day 1). For statistical evaluations (e.g. descriptive summaries) of post-baseline data summarised by visit, or by visit and timepoint, only measurements at scheduled visits or timepoints are considered. If a measurement is repeated at a scheduled visit or time point, then only the latest retest result will be used in calculation of the statistical summary. All data – including from unscheduled measurements – will be included in the listings, and used in the calculation of minimum or maximum value over the course of the study, and in the potential identification of adverse events.

Any cohort that does not reach the Stage I analysis (i.e. does not reach 12 eligible and evaluable patients), will not be presented for statistical analysis per se. (This does not preclude that some or all patients within such cohorts may be included in cross-cohort analyses.)

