4.5.4 Vital Signs

Vital signs will include measurements of respiratory rate, pulse rate, and systolic and diastolic blood pressures while the patient is in a seated position and temperature.

For first infusion of study treatment, the patient's vital signs must be determined within 60 minutes before the infusion; during, and after the infusion if clinically indicated. For subsequent infusions, vital signs will be collected within 60 minutes before infusion and at the end of the infusion, if clinically indicated. Patients will be informed about the possibility of delayed post-infusion symptoms and instructed to contact their study physician if they develop such symptoms.

Blood oxygen saturation will be measured at time points specified in the Schedule of Assessments (see [Appendix 1](#)) by pulse oximetry.

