9. Complete physical examination at screening and treatment discontinuation visit and limited physical examination during treatment. At baseline, physical examination should be done within 3 days prior to the first drug administration (Day 1) See Section 4.5.3.
10. Vital signs include heart rate, respiratory rate, blood pressures, and temperature. At baseline, vital signs should be done within 3 days prior to the first drug administration (Day 1). For first infusion of study treatment, the patient's vital signs should be determined within 60 minutes before the infusion; during, and after the infusion if clinically indicated. For subsequent infusions, vital signs will be collected within 60 minutes

Appendix 1

Schedule of Assessments (cont.)

before infusion and at the end of the infusion, if clinically indicated. Patients will be informed about the possibility of delayed post-infusion symptoms and instructed to contact their study physician if they develop such symptoms.

11. ECG recordings will be obtained during screening and as clinically indicated at other time points. ECG should be done during screening period (within 35 day from Day 1), not needed to be repeated at D1. Patients should be resting and in a supine position for at least 10 minutes prior to each ECG collection.
12. Hematology consists of CBC, including RBC count, hemoglobin, hematocrit, WBC count with automated differential (neutrophils, lymphocytes, eosinophils, monocytes, basophils, and other cells), and platelet count. A manual differential can be done if clinically indicated. See Section 4.1.1 for a list of laboratory results obtained within 3 days prior to the first study treatment.
13. Laboratory tests that should be done within 3 days prior to the first drug administration (Day 1): Absolute neutrophil count (ANC), lymphocyte count, white blood cell counts, platelet count, hemoglobin, serum bilirubin, aspartate aminotransferase (AST), alanine aminotransferase (ALT) and alkaline phosphatase, serum albumin, serum creatinine, international normalized ratio (INR) and activated partial thromboplastin time (aPTT). These tests must meet the eligibility criteria.
The other biochemistry test sodium, potassium, magnesium, chloride, bicarbonate ([if routinely performed on venous blood samples]), calcium, phosphorus, glucose, lactate dehydrogenase and total protein can be done within 35 days from D1.

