4.7.4 Vital Signs and ECG

Vital signs and ECG data will be summarized by visit (for vital signs, by timepoint within visit) and presented together with change from baseline, for “All combined” only.

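### The SAP fixes baseline by calendar date, so a vital sign taken during or after the first infusion on Day 1 becomes that patient's baseline

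*SAP*

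**What the plan says.** SAP section 4 gives one baseline rule for all variables: "Baseline values are determined by the last measurement up to and including date of treatment start (Study Day 1"). The same section sets the reference day: "Study Day 1 will be defined as the first day a patient receives study medication". It also deals with repeats: "If a measurement is repeated at a scheduled visit or time point, then only the latest retest result will be used" in the summary. None of these sentences refers to the time of the infusion, and no later SAP section makes an exception for vital signs.

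Protocol section 4.5.4 sets the collection at the first infusion: "vital signs must be determined within 60 minutes before the infusion; during, and after the infusion if clinically indicated". A pre-infusion reading is therefore required in everyone, and further readings on the same date exist only in some patients. Footnote 10 of Protocol Appendix 1 repeats this schedule and adds: "At baseline, vital signs should be done within 3 days prior to the first drug administration (Day 1").

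SAP section 4.7.4 sets the output: "Vital signs and ECG data will be summarized by visit (for vital signs, by timepoint within visit) and presented together with change from baseline". This is done for all cohorts combined only.

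**The concern.** Study Day 1 contains both pre-dose and post-dose readings. A rule that takes the last value on or before that date will pick a during- or post-infusion reading whenever one exists. The protocol's own wording puts baseline vital signs before dosing, and the SAP does not carry that condition over.

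The error is also selective. The extra readings are taken when clinically indicated, so they probably fall mostly in patients in whom an infusion effect was suspected. Those are the patients whose change from a pre-dose value is of most interest in this table, and they are the ones who would lose their pre-dose reference. All other patients keep the pre-infusion reading as baseline.

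**Working it through.** The plan gives no figure on this point, so there is nothing to reproduce. The check applies the rule literally to the Day 1 schedule.

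**Notation, for one patient**
- P = last reading before the first infusion (required by Protocol 4.5.4).
- L = last reading of any kind on Day 1. L = P if there is no during- or post-infusion reading.
- X = reading at a later visit.
- d = L − P, the shift still present at the last Day 1 reading.

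**Step 1: which value is baseline.** SAP section 4 gives baseline = L. Footnote 10 of Appendix 1 points to P. The two agree unless a during- or post-infusion reading exists.

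**Step 2: effect on later visits.** SAP change = X − L. Pre-dose change = X − P. The difference is (X − L) − (X − P) = P − L = −d, and it is the same at every later visit for that patient.

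**Step 3: effect on Day 1 rows.** If the reading that supplied L is a tabulated timepoint, its change is L − L = 0. If the pre-infusion reading is also shown with a change, that change is P − L, which is not zero although nothing had yet been given.

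**Step 4: effect on a mean.** If a fraction f of the patients in a later-visit summary have such a reading, with mean shift d, the mean change is biased by −f × d.

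**Illustration.** These values are assumed and are not in the documents: systolic pressure 120 mmHg before the first infusion, 95 at the last Day 1 reading, 120 before Cycle 2. Then d = 95 − 120 = −25.

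| | Baseline | Change, last Day 1 reading | Change, Cycle 2 pre-dose |
|---|---|---|---|
| SAP rule as written | 95 | 95 − 95 = 0 | 120 − 95 = +25 |
| Last pre-infusion value | 120 | 95 − 120 = −25 | 120 − 120 = 0 |

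For the mean, again with assumed f:
- f = 5%: −0.05 × (−25) = +1.25 mmHg.
- f = 20%: −0.20 × (−25) = +5 mmHg.

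If the patient were instead followed until pressure was back to 120, then d = 120 − 120 = 0 and the bias disappears. The error depends on the last Day 1 reading, not on the most abnormal one.

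**Step 5: do other SAP rules prevent this?** The latest-retest rule does not protect the earlier, pre-dose value. SAP section 4 restricts by-visit and by-timepoint summaries to scheduled measurements, but that restriction is stated for post-baseline data; the baseline sentence has no such limit. If clinically indicated readings count as unscheduled, one of them could set the baseline and yet not appear as a row. The zero-change row would then not exist, but the −d shift would remain. The documents do not say which way these readings are classified.

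**The case against.** The strongest defence is that this is loose wording and not a planned post-dose baseline. Footnote 10 puts baseline vital signs before dosing, so the SAP's inclusion of the treatment-start date may be meant only to let the same-day pre-infusion reading count. Protocol section 3.1 itself labels Day 1 as baseline. That is a plausible account of the intent. But section 3.1 names a day, not a reading within it, and a programmer following the SAP sentence would take the later value. The text still needs correcting.

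The rest of the defence limits the consequences, and most of it stands. A reader might infer three stronger things that the documents do not support:

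- *That the safety output cannot show the acute effect of the first infusion.* SAP 4.7.4 presents observed values by timepoint alongside the changes, and the baseline rule does not alter observed values. Infusion-related reactions are recorded as adverse events, with their signs and symptoms on a dedicated form (Protocol 5.3.5.13). Vital-sign abnormalities that are symptomatic, lead to intervention or treatment change, or are judged clinically significant are reportable (5.3.5.5). Events suggesting infusion-reaction syndromes are of special interest (5.2.3), and SAP 4.7.2 summarises and lists events of special interest.
- *That every patient with a post-infusion reading will show a zero change on Day 1.* This requires the reading to be a tabulated timepoint, which cannot be settled without the case report form or table shells.
- *That later changes are wrong by the full acute change.* They are wrong only by what remains at the last Day 1 reading, which may be small after recovery.

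Listings do not fill the gap: SAP section 4 says listings will hold all data, but the SAP history records that most were removed, and no vital-sign listing is named among those that remain in section 4.7.2.

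**Conclusion.** The point holds in a limited form. As written, the SAP rule takes a post-dose vital sign as baseline in any patient with a during- or post-infusion reading on Day 1, and this conflicts with footnote 10 of Protocol Appendix 1. In those patients all later changes from baseline are shifted by the pre-infusion reading minus the last Day 1 reading. A zero change at the last Day 1 reading follows only if that reading is tabulated.

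The affected output is the descriptive change-from-baseline part of the combined vital-sign summary. The same sentence would catch an ECG recorded after dosing on Day 1, but footnote 11 calls for ECGs after screening only when clinically indicated. No test, stage decision, non-progression rate or other efficacy result uses these values. The number of affected patients is not in the documents, so the true bias cannot be stated; the +1.25 to +5 mmHg range rests wholly on the assumed shift and fractions. This is a minor correction, but it corrects a stated rule and does not merely add detail.

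**What to change.** Replace the baseline sentence in SAP section 4 with wording such as: *Baseline is the last measurement taken before the start of the first infusion. For vital signs on Day 1 this is the pre-infusion timepoint; readings taken during or after the first infusion are post-baseline. Where clock time is not recorded, the timepoint label decides.*

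In section 4.7.4, also say whether clinically indicated Day 1 readings are treated as scheduled timepoints, so that it is clear whether they appear in the table.

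The cost is one or two SAP sentences and a filter on the timepoint that section 4.7.4 already uses for its summaries. No new data are needed, and the SAP would then agree with footnote 10.
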